Training will take place twice a week, beginning with a dynamic warm-up of the lumbar extensor for 120s, followed by three sets of resistance training lasting 120s, 120s, and 150s respectively, and concluding with a final set of dynamic recovery lasting 60s. 30-second recovery will be provided between every set. A low load will be used for the warm-up and recovery. The initial load is based on the maximum isometric force and subsequently increased until volitional fatigue. Repetitions will be executed by taking three seconds from complete flexion to complete extension, ensuring standardization at 20 repetitions per minute. A metronome with 40 beats per minute will provide audible feedback. The ILEX machine emits an audible signal upon completion of each phase of the repetition to guarantee a complete range of motion (ROM) is achieved. Subsequent to every training session, participants will be requested to provide their effort (RPE-E) and discomfort (RPE-D) values.

Baseline (BL) measurements are conducted before the initiation of training, and two follow-up measurements (F/U 1 and F/U 2) carried out after the sixth and twelfth session, with a minimum break of 48 hours after the last training session to ensure proper recovery and to prevent inaccuracies in muscle thickness measurement arising due to acute edema. At BL, participants need to give written informed consent and be familiarized with the ILEX machine and Category-Ratio-Scale (CR10) for the assessment of perceived effort and discomfort as well as a 9-point Likert scale for thermal sensation and 5-point scale for comfort. BL assessment include epidemiological data such as age, sex, height, and weight. Physical activity is assessed using the self-administered short German version of the International Physical Activity Questionnaire (IPAQ) with a "last 7 d recall" (IPAQ Research Committee, 2005) at BL, F/U1 and F/U2. At all three measurements (BL, F/U 1, F/U 2), the lumbar extensor musculature thickness (M. erector spinae), the maximum ROM, the maximum voluntary isometric contraction, the lower back flexibility, and the isometric back extension endurance are measured. Skin temperature is measured using an infrared thermal imaging (FLIR A615 series, Emitec Industrial, Rotkreuz, Switzerland) after the first and final diathermy treatment.

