4 STUDY POPULATION AND STUDY PROCEDURES

4.1 Inclusion and exclusion criteria, justification of study population

Power analysis was conducted with G*power to determine participants numbers (n) calculating a treatment effect size of 0.46 from previous research with the comparable MedX ILEX device in healthy volunteers (Fisher et al., 2018). The priori sample size was calculated ($\alpha = 0.05$; effect size = 0.46; test family = F test, and statistical test = analysis of variance (ANOVA) repeated measures, within-between interaction; number of groups = 2; number of measurements = 3; power = 0.8) and revealed $n = 10$ participants. 14 healthy volunteers will be recruited according to the following criteria:

Study inclusion criteria:

- Healthy (no acute musculoskeletal injuries or illness),
- Pain free,
- Sufficient understanding of the German language,
- Able to give informed consent as documented by signature,
- Between 18 and 50 years old

Study exclusion criteria:

- Pregnant (urine pregnancy test is given to participating woman) or lactating women,
- Medication,
- Previous surgery in the lumbar spine,
- Knee or hip disorders contraindicating the use of ILEX device,
- Currently experiencing LBP,
- History of LBP or lumbar spine pathologies or known deformities,
- Psychological or neuromuscular disorders, spinal pathologies or any other injuries or illness that would restrict normal movement,
- Previous (last 12 months) or current isolated training of the lumbar extensor.

This study will be conducted in healthy people. The risk of injury will be low in this population group.

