5 STATISTICS AND METHODOLOGY

5.1. Statistical analysis plan and sample size calculation

A priori sample size calculation was performed using G*power (Version 3.1, Franz Faul, Germany) to determine participants numbers (n) ($\alpha = 0.05$; effect size = 0.46; test family = F test, and statistical test = analysis of variance (ANOVA) repeated measures, within-between interaction; number of groups = 2; number of measurements = 3; power = 0.8) and revealed n = 10 participants. The effect size was estimated based on previous research with a comparable ILEX device in healthy volunteers (Fisher et al., 2018).

Assumption of normality will be verified using the Shapiro-Wilk test. Mauchly's test will indicate the violation of the assumption of sphericity. Normally distributed data will be analysed applying ANOVA repeated measures with within-between interactions to compare the means of each variable over the three repeated observations (within) and between the intervention and sham group (between). Not normally distributed data will be examined using non-parametric statistics (Friedman's two-way ANOVA). Post hoc Bonferroni test correction will be applied. Probability values $p < 0.05$ will be considered statistically significant.

Men and women are included in this study and will be part of the randomization process. The planned sample size of this study does not allow for gender-specific analysis. A gender difference analysis will have to be part of a future study.

Analyses will be performed using RStudio Team (2023) (RStudio: Integrated Development Environment for R. Boston, MA) and IBM SPSS Statistics (Version 27, IBM Corp., Armonk, NY, USA).

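### Baseline is analysed as one of three outcome levels and never adjusted for, which costs the arm comparison some precision at the correlation implied by n = 10 and carries chance baseline imbalance into the estimate

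*Combined protocol and SAP*

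**What the plan says.** Section 5.1 analyses every normally distributed variable by "ANOVA repeated measures with within-between interactions to compare the means of each variable over the three repeated observations", with intervention versus sham as the between-subject factor. Sections 3.4 and 4.3 identify the observations as BL, F/U1 (after session 6) and F/U2 (after session 12). Section 3.4 states that "Baseline (BL) measurements are conducted before the initiation of training", so the first of the three levels precedes any diathermy.

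Section 5 names no covariate. The word appears only in section 3.3, where sex is a covariate for block randomisation.

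The sample size in section 5.1 rests on the same model: "effect size = 0.46; test family = F test", "statistical test = analysis of variance (ANOVA) repeated measures, within-between interaction", "number of groups = 2; number of measurements = 3; power = 0.8", which "revealed n = 10 participants". The correlation between repeated measures is not given. Section 4.1 recruits 14 people, and section 5.2 does not replace drop-outs.

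The between-arm hypotheses in section 3.1 concern a difference in improvement. The plan does not say which F test or contrast decides them.

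**The concern.** Baseline can serve as a response level or as a covariate. As a response level, the comparison of arms from BL to a follow-up is a difference of change scores, which fixes the baseline coefficient at 1. Under equal variances the best coefficient is the correlation, so at a correlation near 0.5 a change score over-corrects. An arm that happens to start stronger then appears to gain less.

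The planned sentence also compares arms over all three visits. Diathermy cannot have affected BL, so that group main effect understates any real effect.

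At stake is precision in a trial of 14 that cannot be enlarged later. Every baseline value needed is already collected.

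**Working it through.** **Inputs.** From section 5.1: alpha 0.05 ("Probability values $p < 0.05$ will be considered statistically significant"), f = 0.46, 2 groups, 3 measurements, target power 0.80. From section 4.1: N = 14. Assumed: 7 per arm (no allocation ratio is stated), compound symmetry, normal data, and an illustrative effect at F/U2 of 1.6 SD of change. At correlation 0.5 the SD of change is √(2(1 − 0.5)) = 1 SD of the outcome.

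**1. The plan's own figure.** For the within-between interaction, λ = f²·N·3/(1 − ρ) on 2 and 2(N − 2) df. At ρ = 0.5 and N = 10, λ = 0.2116 × 30/0.5 = 12.70 and power is 0.833. N = 8 gives 0.709. So n = 10 reproduces at ρ = 0.5, and it is the smallest even N for ρ from about 0.46 to 0.59. At N = 14 and ρ = 0.5, power is 0.95.

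**2. Variance against change from baseline.** The large-sample ratio of ANCOVA to change-score variance is (1 − ρ²)/(2(1 − ρ)) = (1 + ρ)/2. Estimating the slope multiplies it by (N − 3)/(N − 4). At ρ = 0.5 and N = 14 this is 0.75 × 11/10 = 0.825, about 18% less variance (simulated 0.82 to 0.83).

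**3. Against the planned analysis.** The repeated-measures contrast from BL to F/U2 uses pooled error on 2(14 − 2) = 24 df. A two-visit change-score t-test has only 12 df and is not what is planned. Simulated results at ρ = 0.5, effect 1.6 SD of change:

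- Pooled contrast to ANCOVA at F/U2: mean 95% CI half-width 1.09 to 1.04 SD; power about 82% to 85%.
- 2-df omnibus interaction F to ANCOVA: power 71% to 85% if the effect grows linearly, 84% to 85% if it is complete by F/U1. The linear gap is mostly due to using 1 df instead of 2, since the pooled contrast alone reaches 82%.

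**4. Sensitivity to the correlation (7 per arm, ANCOVA against pooled contrast).**

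| ρ | CI half-width ratio | Power change, points |
|---|---|---|
| 0.5 | 0.955 | about +3 |
| about 0.6 | 0.98 | about nil |
| 0.7 | 1.016 | about −1 |
| 0.8 | 1.046 | about −4 |
| 0.9 | 1.077 | about −6 |

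With 5 per arm at ρ = 0.5 there is no gain: power is about 65 to 66% either way, and the half-width is 1.345 for ANCOVA against 1.324.

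**5. Chance imbalance.** Given a baseline difference d between arms, the change-score estimate is off by −(1 − ρ)d in expectation. The SD of d is √(2/7) = 0.535 SD, so under simple randomisation the chance that |d| exceeds 0.5 SD is 35%. In simulated trials where the diathermy arm started more than 0.5 SD higher, the change score was off by −0.40 SD on average at ρ = 0.5 and −0.16 at ρ = 0.8. ANCOVA was off by about 0.00 at both.

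**6. Group main effect.** A constant effect δ after treatment averages to (0 + δ + δ)/3 = 2δ/3. At f = 0.46, N = 14 and ρ = 0.5, the main effect has power 0.66 (linear) or 0.78 (plateau), against 0.95 for the interaction.

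**7. Validity.** With no effect, all these tests reject in about 5% of simulated trials.

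**The case against.** The strongest reply is that the planned interaction already answers section 3.1. Baseline has to be in that model as the reference for improvement, and the test holds its level. This stands. A reader might infer that the planned test is biased or invalid, and the documents do not support that. Averaged over randomisation it is unbiased; what remains is lost precision and sensitivity to the particular imbalance that occurs.

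A second reply concerns size, and it also stands. Against a 12-df change-score t-test, power would rise from 79% to 85% and the half-width would fall from 1.14 to 1.04 SD. A reader might quote those figures, but section 5.1 plans a three-visit ANOVA, whose pooled error gives a tighter comparator. That advantage depends on sphericity, which the plan checks with Mauchly's test.

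Third, the correlation is back-solved. The primary outcome is absolute force in men and women aged 18 to 50, which could push it higher. If the within-sex correlation were 0.5 to 0.7 and the sexes differed by 1 to 2 SD (assumptions), the overall value would be 0.60 to 0.85, where adjustment gains nothing or loses against the pooled contrast.

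Fourth, the 35% figure ignores randomisation by sex. If sex is balanced and explains 30 to 50% of baseline variance (assumption), it falls to 26 to 19%, so 35% is an upper figure.

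Finally, the group main effect is not the test of section 3.1. That is correct, but the plan does not name the deciding test, so the main effect could still be reported as evidence on diathermy.

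**Conclusion.** The point holds as a modest matter of efficiency and of protection against imbalance, not of validity. At the correlation of about 0.46 to 0.59 that reproduces n = 10, adjusting for baseline is at least as precise as the planned contrast. At 0.5 with 7 per arm, the interval is about 4.5% narrower and power about 3 points higher.

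The result rests on equal arms, compound symmetry and an undocumented correlation. It reverses from about 0.7 upward and disappears with 5 per arm. At the planned f = 0.46, power with 14 people is already about 0.95, so the gain matters mainly for smaller effects. Protection from the imbalance that actually occurs remains at higher correlations, but the error it removes shrinks in proportion to 1 − ρ.

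**What to change.** In section 5.1, for each endpoint measured at BL, F/U1 and F/U2:

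- Make the between-arm analysis a model with F/U1 and F/U2 as outcomes and that endpoint's own BL value as covariate, with terms for arm, visit, arm by visit and baseline by visit. With complete data and an unstructured covariance, its F/U2 contrast is the ANCOVA at F/U2 used above.
- Name the adjusted arm difference at F/U2, after 12 sessions, with its 95% CI, as the deciding contrast.
- Keep the pre-post analysis for the within-group training hypotheses, which need BL as a level.
- State that the group main effect of a three-visit ANOVA is not evidence on diathermy.
- In the sample-size paragraphs of sections 4.1 and 5.1, say that n = 10 was computed for the interaction test and give the assumed correlation.

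The cost is wording and no new data. The statistical price is one residual degree of freedom for the covariate and, against the pooled repeated-measures contrast, about 4 to 6 points of power if the correlation is 0.8 to 0.9.

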3 STUDY OBJECTIVES AND DESIGN

3.1 Hypothesis and primary objective

The main aim of this study is to investigate the effect of back extensor strength after 6 weeks of ILEX training and diathermy therapy.

- H_0 : 6 weeks of resistance training on the ILEX machine does not improve lumbar extensor muscle strength.
- H_1 : 6 weeks of resistance training on the ILEX machine improves the strength of the lumbar extensor muscle.
- H_0 : There is no difference in the improvement in lumbar extensor muscle strength between those who receive a microwave diathermy treatment before each resistance training session and those in the sham group.
- H_1 : Individuals who receive a microwave diathermy treatment prior to each resistance training session improve their lumbar extensor muscle strength more than those in the sham group.

Secondary objectives are to examine the development of M. erector spinae thickness, isometric back extension endurance, and lumbar extensor flexibility after 6 weeks of resistance training and diathermy therapy.

- H_0 : 6 weeks of resistance training on the ILEX machine does not enhance the thickness of the M. erector spinae.
- H_1 : 6 weeks of resistance training on the ILEX machine enhances the thickness of the M. erector spinae.
- H_0 : There is no difference in the increase of the thickness of the M. erector spinae between those who receive a microwave diathermy treatment before each resistance training session and those in the sham group.
- H_1 : Individuals who receive a microwave diathermy treatment prior to each resistance training session enhance the thickness of the M. erector spinae more than those in the sham group.
- H_0 : 6 weeks of resistance training on the ILEX machine does not improve isometric back extension strength endurance.

- H_1 : 6 weeks of resistance training on the ILEX machine improves isometric back extension strength endurance.
- H_0 : There is no difference in the improvement of the isometric back extension strength endurance between those who receive a microwave diathermy treatment before each resistance training session and those in the sham group.
- H_1 : Individuals who receive a microwave diathermy treatment prior to each resistance training session improve the isometric back extension strength endurance more than those in the sham group.
- H_0 : 6 weeks of resistance training on the ILEX machine does not increase lumbar ROM.
- H_1 : 6 weeks of resistance training on the ILEX machine increases lumbar ROM.

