3.3 Study design

This is a monocentric clinical trial with minimal risks and burden of the risk class A (KlinV, Art. 20). A block randomization with covariates (i.e. sex) is used. The preheating is done as a single blinded randomized controlled trial (RCT) with the sham group receiving a 10-minute diathermy treatment with the Tecar device turned off and not sending radiofrequency before each exercise session. The intervention group undergoes a 10-minute treatment with the Tecar device to induce 448kHz capacitive monopolar radiofrequency and facilitate warming up of deep tissues. In order to be able to carry out a single-blind situation as far as possible, the test subjects are not told that the therapy causes heat of the deep tissue and that this is the factor being investigated. Instead, we speak of high-frequency Tecar therapy and its known use to promote tissue healing processes.

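### The fallback for non-normal data cannot test diathermy against sham, and sex, a randomisation factor, is left out of the group-by-time model

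*Combined protocol and SAP*

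**What the plan says.** Section 3.1 sets two primary hypotheses. The first is that ILEX training improves strength over 6 weeks. The second is a group comparison, with the null "There is no difference in the improvement in lumbar extensor muscle strength between those who receive a microwave diathermy treatment" and those in the sham group.

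On allocation, section 3.3 states: "A block randomization with covariates (i.e. sex) is used". Section 5.1 repeats that both sexes enter the randomisation.

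On analysis, section 5.1 gives one parametric model, a repeated-measures ANOVA used to "compare the means of each variable over the three repeated observations (within) and between the intervention and sham group (between". Its factors are time and group; no endpoint has a sex term. For the rest, "Not normally distributed data will be examined using non-parametric statistics", and the only method named is Friedman's two-way ANOVA.

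On gender, section 5.1 says that the sample is too small for analysis by gender and adds: "A gender difference analysis will have to be part of a future study". Section 10 closes by committing the team to analysing gender effects and publishing them.

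**The concern.** Three things do not fit together.

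- **The fallback.** Friedman's test ranks each person's three visits and asks whether the visits differ. It carries neither group nor sex. If the primary endpoint takes this branch, the plan has no test of diathermy against sham, and a significant result can come from training alone. Run separately in each arm, the test invites the misreading that diathermy works because one arm was significant and the other was not.
- **The sex term.** Analysis normally follows the factor used to randomise. If men and women gain different amounts of strength, that variation goes into the error term of the group-by-time test.
- **The gender statements.** Sections 5.1 and 10 cannot both be followed.

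**Working it through.** **Inputs from the documents.** N = 14 (sections 3.4 and 4.1); 2 groups, 3 visits, alpha 0.05, effect size 0.46, power 0.8, calculated n = 10 (section 5.1).

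**Assumptions.** 7 per arm; 3 men and 4 women in each arm unless stated; normal data with equal correlation between visits of 0.5, 0.7 or 0.85; all sex differences and training gains. The documents give none of these.

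**1. The plan's own figure.** Reading 0.46 as Cohen's f, with correlation 0.5 and sphericity:

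- lambda = f² × N × 3 / (1 − correlation); error df = (N − 2) × 2.
- N = 10: lambda = 0.2116 × 10 × 3 / 0.5 = 12.7, df 2 and 16, power 0.833. The stated n = 10 is reproduced.
- N = 14: lambda = 0.2116 × 14 × 3 / 0.5 = 17.8, df 2 and 24, power 0.952.
- N = 14 with sex and sex x time: df 2 and 22, power 0.950.

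**2. Friedman's test.** With n people, k = 3 visits and rank sums R_j, Q = 12 / (n k (k+1)) × ΣR_j² − 3n(k+1). For n = 14 this is ΣR_j² / 14 − 168. Arm appears nowhere in it. Simulation with the same training gain in both arms and no diathermy effect, over correlations 0.5-0.85:

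| Training gain (SD of level) | Significant, all 14 | Run per arm: exactly one arm significant |
|---|---|---|
| 0.5 | 25-69% | 24-47% |
| 1.0 | 77-100% | 17-49% |

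The branch is reachable. Section 5.1 does not say what the Shapiro-Wilk test is applied to. If it were run in each of the 6 group-by-visit cells, normal data would fail at least once with probability 1 − 0.95⁶ = 0.26, treating the cells as independent.

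**3. Sex in the ANOVA, near-balanced splits.** The interaction is tested on differences between visits, so a constant sex difference in strength level cancels. A sex main effect therefore changes nothing; only sex x time matters. Power is shown for a diathermy effect of 1 SD of level at F/U2 and half that at F/U1, which is f = √(3.5 × 0.5 / 42) = 0.204. Entries are for correlations 0.5 / 0.7 / 0.85.

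| Sex difference (SD of gain) | As planned | With sex x time |
|---|---|---|
| 0 | 0.333 / 0.515 / 0.827 | 0.329 / 0.509 / 0.824 |
| 0.5 | 0.316 / 0.501 / 0.817 | 0.328 / 0.513 / 0.825 |
| 1.0 | 0.27 / 0.45 / 0.77 | 0.33 / 0.51 / 0.82 |

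At 1 SD the planned test's type I error is 3.2-3.6%, so it is conservative. At the protocol's f = 0.46 and correlation 0.5, power is 0.928 against 0.947 at 1 SD (loss 0.02) and 0.845 against 0.949 at 2 SD (loss 0.10).

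**4. Uneven splits (correlation 0.7).** If gains do not differ by sex, adjusting costs 0.005 power at 3 vs 3 men, 0.015 at 3 vs 4, 0.04 at 2 vs 4 and 0.08 at 0 vs 2. If they do differ, the unadjusted test at 0 vs 2 men has type I error of 5.9% at 1 SD of gain and 8.0% at 2 SD.

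**5. A replacement that works.** With 3 men and 4 women per arm and per-sex totals fixed, there are C(6,3) × C(8,4) = 20 × 70 = 1,400 allocations. Re-randomisation within sex of the sex-adjusted group x time statistic, at correlations 0.5 / 0.7:

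| Visit error | Type I error | Power, re-randomisation | Power, F test |
|---|---|---|---|
| Normal | 4.8 / 4.9% | 0.33 / 0.49 | 0.33 / 0.50 |
| Lognormal | 5.0 / 5.5% | 0.49 / 0.67 | 0.45 / 0.63 |

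The block size is not given. With blocks of 2 within sex there would be 2³ × 2⁴ = 128 allocations and a smallest p-value of 2/128 = 0.016, which is still below 0.05.

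**The case against.** The strongest objection is that the sex term is close to a matter of preference. The planned interaction test matches the second primary hypothesis, and any benefit from adjusting needs a sex difference in gain for which the documents give no figure. Adjustment breaks even near 0.3 SD of gain, and with an uneven split it can cost more than it returns. Section 5.1 also limits gender analysis deliberately. Most of this stands, and it is why sex comes second here. The limit in section 5.1, however, concerns analysis by gender, not adjustment for a randomisation factor, and very uneven splits are where leaving sex out can push the error rate above 5%.

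The Friedman defect is not about sex and would exist in a single-sex trial. That is true, and it is why it leads. It is also fair that Friedman's test is a proper test of the first primary hypothesis, change over time, so it should not be removed altogether.

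Three stronger readings are tempting and are not supported:

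- A reader might infer that omitting sex invalidates the main analysis or biases it towards diathermy. Level differences cancel, and with near-balanced splits the test is conservative.
- A reader might infer that the sponsor intends to claim a diathermy effect from Friedman's test. The plan does not say so; it simply names no other test for that branch.
- A reader might infer from "Post hoc Bonferroni test correction will be applied" that groups will be compared on strength level at F/U2, where a sex difference would not cancel. No comparisons are listed, so this cannot be concluded.

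**Conclusion.** The point holds, in this order of weight.

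1. **Wrong as written:** in the non-normal branch, the second primary hypothesis has no test. This follows from the form of Friedman's test and needs no assumption. The simulated rates show how easily training alone gives a significant result; they rest on the assumed gains and correlations.
2. **Near-free improvement:** sex should enter the model as sex and sex x time. With near-balanced splits the gain is about 0.01 power at a sex difference of 0.5 SD of gain and 0.05-0.06 at 1 SD for a 1 SD diathermy effect. At f = 0.46 and correlation 0.5 it is about 0.02 at 1 SD and 0.10 at 2 SD. With a very uneven split it also restores the 5% error rate. All the sex differences are assumed.
3. **Contradiction in the text:** sections 5.1 and 10 on gender analysis.

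The parametric group-by-time test remains usable, so this is a change the sponsor should make rather than a fatal fault.

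**What to change.** In section 5.1:

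- **Non-normal branch.** If model residuals are clearly non-normal, test the group difference by re-randomisation of the sex-adjusted group x time statistic, permuting group within sex according to the actual block scheme. Keep Friedman's test as the inferential test of change over time, for the first primary hypothesis, and state that it will not be used to conclude on diathermy.
- **Parametric branch.** Keep group x time as the test and add sex and sex x time as adjustment terms. Use the same model for the other endpoints measured at BL, F/U1 and F/U2.
- **Uneven splits.** State in advance what happens to the sex term. The simplest rule is to keep it whatever the split, unless all participants are of one sex. Since drop-outs are not replaced (section 5.2), the final split may differ from the randomised one.

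In sections 5.1 and 10, state that sex is an adjustment term only and that any results by sex are descriptive.

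The cost is wording and no new data, since sex is already recorded at baseline (section 4.3). Adjustment uses two error df (24 to 22). If gains do not differ by sex, that is about 0.005 power with even splits, rising to about 0.04 at 2 vs 4 men and 0.08 at 0 vs 2 (correlation 0.7).
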